If the laboratory abnormality induces clinical signs or symptoms, or requires therapeutic intervention, and satisfies the criteria defined in [Section 10](#) Safety reporting, then the diagnosis or medical condition must be entered on the AEs page of the subject's eCRF and any treatment necessary should be documented. If the laboratory abnormality is the primary reason for an unforeseen hospitalization or otherwise fulfills the seriousness category of an AE, then the procedure for rapid notification of SAEs must be followed.

Likewise, if the laboratory abnormality leads to discontinuation of the study drug, the subject must be followed until the abnormality resolves or until it is judged to be permanent. This investigation may include continued monitoring by repeat laboratory testing or by performing additional laboratory tests as deemed necessary by the investigator or the Sponsor's medical monitor.

For child bearing potential females only, serum pregnancy testing will be performed at screening (visit 500), and End of Study visit (Visit 599). Please see details in [Section 8.4.2](#).

A table, which provides the maximum, allowable blood-draw volumes by weight, can be found in [Appendix 8](#).

There are countries where plasma potassium is used instead of serum potassium for routine clinical care. Plasma potassium can be used instead of serum potassium in this study. Serum potassium thresholds in the study protocol, including those values cited in [Appendix 1](#) and [Appendix 7](#) can be converted to plasma potassium thresholds for the study by subtracting 0.4 mmol/L from the serum potassium threshold.

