> 2 $\times$ ULN (in the absence of known bone pathology)	
 
Repeat LFT within 48 hours
 
If elevation persists, establish causality
 
Complete liver eCRF
 
	Investigator discretion Monitor LFT within 1 to 4 weeks or at next visit
TBL (isolated)		
> 2 $\times$ ULN (in the absence of known Gilbert syndrome)	
 
Repeat LFT within 48 hours
 
If elevation persists, discontinue the study drug immediately
 
Hospitalize if clinically appropriate
 
Establish causality
 
Complete liver eCRF
 
	ALT, AST, TBL, Alb, PT/INR, ALP and $\gamma$ GT until resolution c (frequency at investigator discretion) Test for hemolysis (e.g. reticulocytes, haptoglobin, unconjugated [indirect] bilirubin)
> 1.5 to $\leq$ 2 $\times$ ULN (patient is asymptomatic)	
 
Repeat LFT within the next week
 
If elevation is confirmed, initiate close observation of the patient
 
	Investigator discretion Monitor LFT within 1 to 4 weeks or at next visit
Jaundice	
 
Discontinue the study treatment immediately
 
Hospitalize the patient
 
Establish causality
 
Complete liver eCRF
 
	ALT, AST, TBL, Alb, PT/INR, ALP and $\gamma$ GT until resolution c (frequency at investigator discretion)
Any AE potentially indicative of a liver toxicity	
 
Consider study treatment interruption or discontinuation
 
Hospitalization if clinically appropriate
 
Establish causality
 
	Investigator discretion

Criteria	Actions required	Follow-up monitoring
	

• Complete liver eCRF

	

aElevated ALT/AST > 3 × ULN and TBL > 2 × ULN but without notable increase in ALP to > 2 × ULN  
b(General) malaise, fatigue, abdominal pain, nausea, or vomiting, or rash with eosinophilia  
cResolution is defined as an outcome of one of the following: (1) return to baseline values, (2) stable values at three subsequent monitoring visits at least 2 weeks apart, (3) remain at elevated level after a maximum of 6 months, (4) liver transplantation, and (5) death.

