#### Action situation

If a patient eGFR\* decreases by  $\geq 50\%$  from baseline of the core study (i.e. Visit 301 for Part 2) (or if serum creatinine concentration rises above 3 mg/dL (265  $\mu$ mol/L), the investigator will check for potentially reversible causes of renal dysfunction (see above). If the investigator judges that study medication has to be stopped, he/she will have to contact the Novartis medical monitor or his/her designee. Thereafter, serum creatinine assessments will have to be repeated at least each week until levels return to acceptable values. If study medication was stopped, every effort will be done to restart it again, according to clinical conditions.

\*eGFR is calculated using a modified Schwartz formula for subjects  $<18$  years.

For subjects  $\geq 18$  years, an adult formula for eGFR will be utilized (Reference: Novartis Nephrology Guidance document)

[figure not shown]

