2.1.1 General definitions

Study treatment is sacubitril/valsartan.

The date of first administration of study treatment is the day of the first dose of sacubitril/valsartan.

The date of last administration of study treatment is the day of the last non-zero dose of sacubitril/valsartan.

Study day is defined as actual date – date of first administration of study treatment + 1.

Baseline is defined as last non-missing value before starting treatment, where for the same parameter, central laboratory result takes precedence over local laboratory result; in general values are obtained at the baseline visit (501), with the exception of urinalysis and complete laboratory, which are obtained at the screening visit (500). In case these two visits happened on the same day, results from the central laboratory will be considered as baseline values. Note that per protocol, in the case that visit 500 and, if applicable visit 501, is scheduled within 14

days of the PANORAMA-HF End of Study visit (Visit 416), the assessment results from PANORAMA-HF End of Study visit can be used as screening/baseline.

The **study period** starts with the date of screening visit (500) and ends with the date of end-of-study (EOS) or premature study discontinuation (PSD) visit (599).

Treatment period starts with the date when the first dose of study treatment is given (visit 501, unless no dose is given at that visit) and ends with the date of treatment disposition. In the case that no EOS visit was undertaken (e.g., because the patient died or withdrew from the study without such a visit), the treatment period ends with the death/withdrawal date or the last dose taken as reported in the DAR page. Subjects who permanently discontinued study drug should be scheduled for the discontinuation study Visit 599. Note that after a consecutive 3-month interruption of study treatment, subject should be discontinued from the study and should be seen at the site for Visit 599.

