2.8.3 Laboratory data

Complete and abbreviated laboratory evaluations are described in [Table 2-2](#). Complete laboratory evaluations (hematology, blood chemistry, and urine) are performed at screening (Visit 500), and subsequently every 12 months from Visit 501 until End of Study (Visit 599); these analyses are performed at central laboratory.

Abbreviated safety laboratory evaluation consists of serum sodium, potassium, creatinine, and eGFR. Abbreviated laboratory evaluations are performed every 12 months starting from visit at 6 months (Visit 507). In addition, abbreviated laboratory assessments are performed at up-titration visits (visits 501, 502, 503, 504 and 505, as applicable), and unscheduled visits with planned dose level changes; these analyses can be performed at central or local laboratories. Laboratory data will be reported for the treatment period. Note that a window of 5-day will be used to include laboratory data performed within 5 days after the discontinuation of treatment.

Table 2-4 Laboratory Assessments

Hematology	Biochemistry	Urine measurements**
Hematocrit	Alanine aminotransferase (ALT)	Specific gravity
Hemoglobin	Albumin (Alb)	pH
Platelet count	Alkaline phosphatase (ALP)	Glucose
Red blood cell count (RBC)	Aspartate aminotransferase (AST)	Protein (Total)
White blood cell count (WB)	Blood urea nitrogen (BUN)	Ketones
WBC differential	Calcium	Bilirubin
	Magnesium	Urobilinogen
	Phosphate	Hemoglobin (blood)
Red blood cell distribution width (RDW)	Chloride	Leukocyte esterase
Mean corpuscular volume (MCV)	Creatinine*	Nitrite
Mean corpuscular hemoglobin concentration (MCHC)	Glucose	WBC
	Potassium	RBC sediments
	Sodium	Hyaline casts
	Bicarbonate	Granular casts
	Total bilirubin (TBL)	Waxy casts
	Fractionated bilirubin (if total bilirubin > 2x ULN)	WBC casts
	Total protein	RBC casts
	Uric acid	
	eGFR*	

*Abbreviated laboratory evaluations must include these parameters

**Urinalysis with dipstick includes specific gravity, pH, glucose, total protein, bilirubin, ketones, urobilinogen, nitrite, leukocytes esterase and hemoglobin (blood). Other urine measurements listed are not required. If a urine dipstick is positive, other urine measurements such as a qualitative microscopic determination of WBC, RBC sediments (and casts) should also be measured.

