White Blood Cell Count	x10E3/uL	>50% increase and >ULN; >50% decrease and <LLN.	x10E9/L
Platelet Count	x10E3/uL	>75% increase and >ULN; >50% decrease and <LLN.	x10E9/L
Chemistry			

BUN	mg/dL	>50% increase and >ULN	mmol/L
Creatinine	mg/dL	>50% increase and >ULN	umol/L
Albumin	g/dL	<20	g/L
Glucose	mg/dL	>50% increase and >ULN; (>50% decrease and <LLN) or any value <3.3.	mmol/L
Total Bilirubin	mg/dL	>100% increase and >ULN	umol/L
AST (SGOT)	U/L	>150% increase and >ULN	U/L
ALT (SGPT)	U/L	>150% increase and >ULN	U/L
Sodium	mEq/L	(>5% increase and >ULN) or any value >150; (>5% decrease and <LLN) or any value <125	mmol/L
Potassium	mEq/L	(>20% increase and >ULN) or any value >6; (>20% decrease and <LLN) or any value <3.	mmol/L
Chloride	mEq/L	>10% increase and >ULN; >10% decrease and <LLN	mmol/L
Calcium	mg/dL	>10% increase and >ULN; >10% decrease and <LLN.	mmol/L
Uric Acid	mg/dL	>50% increase and >ULN	mmol/L

Liver events

[Table 2-4](#) provides criteria for liver laboratory triggers and liver events.

The liver laboratory triggers and liver events during the treatment period based on the local laboratory assessments and the central laboratory assessments will be summarized together by criteria and age group, using the numbers and percentages of patients satisfying such criteria.

Table 2-6 Liver event and laboratory trigger definitions

Definition / threshold	
LIVER LABORATORY TRIGGERS	
 • $3 \times \text{ULN} < \text{ALT} / \text{AST} \leq 5 \times \text{ULN}$ • $1.5 \times \text{ULN} < \text{TBL} \leq 2 \times \text{ULN}$
LIVER EVENTS	
 • ALT or AST $> 5 \times \text{ULN}$ • ALP $> 2 \times \text{ULN}$ (in the absence of known bone pathology) • TBL $> 2 \times \text{ULN}$ (in the absence of known Gilbert syndrome) • ALT or AST $> 3 \times \text{ULN}$ and INR > 1.5 • Potential Hy's Law cases (defined as ALT or AST $> 3 \times \text{ULN}$ and TBL $> 2 \times \text{ULN}$ [mainly conjugated fraction] without notable increase in ALP to $> 2 \times \text{ULN}$) • Any clinical event of jaundice (or equivalent term) • ALT or AST $> 3 \times \text{ULN}$ accompanied by (general) malaise, fatigue, abdominal pain, nausea, or vomiting, or rash with eosinophilia • Any adverse event potentially indicative of a liver toxicity*

Definition / threshold

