*These events cover the following: hepatic failure, fibrosis and cirrhosis, and other liver damage related conditions; the non-infectious hepatitis; the benign, malignant and unspecified liver neoplasms

TBL: total bilirubin; ULN: upper limit of normal

Renal events

Renal events are defined using the following two categories of criteria.

1. Serum event:

- a. Serum estimated GFR* decrease $\geq 25\%$ compared to baseline AND eGFR $< 90 \text{ mL/min}/1.73\text{m}^2$
- b. Serum estimated GFR* decrease $\geq 50\%$ compared to baseline

Note that *eGFR is calculated using a modified Schwartz formula for patients <18 years:

$\text{eGFR} (\text{ml/min}/1.73\text{m}^2) = 0.413 \times \text{height (cm)} / \text{serum creatinine (mg/dl)}$.

2. Urine event:

- a. New onset ($\geq 1+$) proteinuria
- b. New onset ($\geq 1+$) hematuria
- c. New onset ($\geq 1+$) glucosuria

The renal events during the treatment period based on the local laboratory assessments and the central laboratory assessments will be summarized together by criteria and age group (and overall), using the numbers and percentages of patients satisfying such criteria.

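### Liver criteria, and less often serum renal criteria, first met more than 5 days after a permanent stop are missing from the SAP's event tables, although adverse events count to last dose + 30 days

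*SAP*

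**What the plan says.** **SAP, laboratory data.** Section 2.8.3 states: "Laboratory data will be reported for the treatment period". It then adds: "Note that a window of 5-day will be used to include laboratory data performed within 5 days after the discontinuation of treatment". The two event summaries in the same section repeat the limit. For the liver: "The liver laboratory triggers and liver events during the treatment period based on the local laboratory assessments and the central laboratory assessments will be summarized". For the kidney: "The renal events during the treatment period based on the local laboratory assessments and the central laboratory assessments will be summarized together". Under SAP 2.1.1 the treatment period "ends with the date of treatment disposition", with a fallback (death, withdrawal or last recorded dose) if there was no end-of-study visit. The SAP specifies no table or listing of laboratory results after the window closes.

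**SAP, adverse events.** Section 2.8.1 counts an event as treatment-emergent up to 30 days after the last dose in the dosing record. Later events go to the adverse-event listing.

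**Protocol, testing after a stop.**
- Section 8.4.1, where a laboratory abnormality leads to discontinuation: "the subject must be followed until the abnormality resolves or until it is judged to be permanent".
- Table 16-4 continues liver tests until resolution, at a frequency left to the investigator. One of several definitions of resolution is "stable values at three subsequent monitoring visits at least 2 weeks apart"; another is persistent elevation after at most 6 months.
- Appendix 4 (Action situation), after the judgement that study medication has to be stopped: "serum creatinine assessments will have to be repeated at least each week until levels return to acceptable values".
- Section 10.2.1 requires liver follow-up findings to be recorded in the CRF.

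**The concern.** Laboratory values are among the primary endpoints (Protocol Table 2-1, SAP 2.5.1), and Table 2-6 is where a liver injury is classified: trigger, event or potential Hy's Law. Classification can change after drug is stopped, because bilirubin or INR may cross its threshold later than the transaminases.

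Follow-up tests carry much of that classification in this study. ALT, AST and bilirubin belong to the complete panel, which is scheduled every 12 months. The abbreviated panel has only sodium, potassium, creatinine and eGFR. INR is in neither routine panel (Protocol Table 8-3, SAP Table 2-4), yet Table 2-6 has a row that needs it. It is measured only in the follow-up after a liver signal.

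Two things are at stake. A child who stopped because of harm may be shown at a lower category than the one finally reached. And Table 2-6 may disagree with the treatment-emergent tables about the same child.

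**Working it through.** The plan gives no figure to reproduce, so the check sets the rules side by side.

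**1. The windows after a permanent stop**

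| Data | Ends at | Counted from |
|---|---|---|
| Laboratory values | + 5 days | discontinuation of treatment |
| Clinical (AE-based) rows of Table 2-6 | end of treatment period | treatment disposition |
| Treatment-emergent adverse events | + 30 days | last dose |
| Liver follow-up under Table 16-4 | resolution, up to 6 months | not stated |

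The first three rows use three different anchors. The 5-day extension is worded for laboratory data only, so it does not extend the clinical rows.

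**2. Is the child who stopped still in the liver table?** Each liver rule in Protocol Table 16-4 that requires stopping is matched by an event row in SAP Table 2-6.

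| Reason for stopping (Table 16-4) | Table 2-6 row already met |
|---|---|
| Potential Hy's Law | Potential Hy's Law |
| ALT or AST > 8×ULN | > 5×ULN |
| ALT or AST > 5 to 8×ULN for over 2 weeks | > 5×ULN |
| ALT or AST > 3×ULN with INR > 1.5 | same |
| ALT or AST > 3×ULN with symptoms | same |
| Persistent bilirubin > 2×ULN | same |
| Jaundice | same |

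A discretionary stop for asymptomatic ALT of 3 to 5×ULN is counted as a trigger. So the child is in the table. Early repeats also count: liver tests preferably within 48 hours (Protocol 10.2.1), and eGFR at 24 to 48 hours and again at 2 to 5 days (Table 16-5), provided they follow the stop directly.

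**3. What is lost: a later criterion.** A child stops permanently for symptomatic ALT > 3×ULN. On day 8 bilirubin first exceeds 2×ULN, with ALT still > 3×ULN and ALP not > 2×ULN. Since 8 > 5, the value is outside the laboratory window. The child stays in the symptomatic-ALT row but is absent from the bilirubin and potential Hy's Law rows. Since 8 ≤ 30, an adverse event reported for the same finding is treatment-emergent.

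**4. Clinical liver criteria.** Jaundice starting on day 10 after last dose is treatment-emergent (10 ≤ 30). It enters Table 2-6 only if the treatment period is still open on day 10. If disposition is dated at the stop, it is not counted. If disposition is dated at a Visit 599 held on or after day 10, it is. The SAP does not settle which.

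**5. Serum renal table.** It has two categories: an eGFR fall of at least 25% with eGFR < 90, and a fall of at least 50%. A child already at 50% from the SAP baseline has no higher category to enter. The remaining case is a child who stops permanently below that level and first meets a criterion after day 5. Tests during temporary interruptions stay inside the treatment period, and Appendix 4 expects efforts to restart.

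**6. How far 30 days reaches.** With the SAP's 30.4375 days per month, 6 × 30.4375 = 182.6 days, and 30 / 182.6 = 16.4%. A 30-day count catches later criteria on the adverse-event timescale, but it will not always reach resolution.

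**The case against.** The strongest case against the point is that the 5-day limit is a dated, deliberate choice made before last patient last visit. The protocol's analysis section asks only for by-visit laboratory summaries, so the liver and renal event tables are SAP additions and no protocol analysis is breached. Different windows for adverse events and laboratory data are not in themselves contradictory. After stopping, a child may start an ACEI or ARB, which can move creatinine. Serious late harm is also reported elsewhere: confirmed potential drug-induced liver injury with no other cause is an SAE, and hepatotoxicity and renal impairment are of special interest, with counts and exposure-adjusted rates based on the 30-day definition.

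All of this stands, and it limits the point. It does not make Table 2-6 correct for the child in step 3, and the SAE route is how the two sets of tables come to differ.

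Three stronger readings are tempting but unsupported:
- **A reader might infer that children stopped for liver injury drop out of the liver table.** Step 2 shows that they do not.
- **A reader might infer that all required follow-up falls outside the window.** The 2-week spacing is part of a definition of resolution, not a test schedule. Weekly creatinine is a minimum frequency, and the early repeats fall inside 5 days.
- **A reader might infer that these tables see only 5 of the 30 adverse-event days.** The anchors differ. If disposition is dated at Visit 599, the cut-off is later than last dose + 5 days.

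**Conclusion.** The point holds in a limited form. As written, the SAP leaves out of Table 2-6 any new or higher laboratory criterion first met more than 5 days after a permanent stop. It also lets Table 2-6 differ from the treatment-emergent tables on jaundice and other AE-based liver criteria. The same gap exists in the serum renal table but should matter less often.

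The effect is on the category reported, not on whether the child is reported at all. The number affected cannot be derived from the documents, and the study is single-arm and descriptive, so no test or error rate is involved. The conclusion assumes that the 5 days run from the actual stop of drug and that follow-up results reach the database. The protocol requires the latter explicitly for liver follow-up and for local laboratory results. This is a cheap improvement rather than a serious flaw.

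**What to change.** - Keep the 5-day rule for the existing counts, by-visit means, shift tables and notable values.
- For the liver-event table (including its AE-based rows) and the serum renal-event table, add a second count to last dose + 30 days, anchored on last dose as for treatment-emergent events.
- In that count, mark criteria first met after day 5, and those met while the child was on an ACEI or ARB.
- List liver and renal follow-up results obtained after day 30, so that the course to resolution is visible.

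The cost is SAP wording and programming on data the protocol already asks sites to obtain; no clinical rule changes. The downside is that some late values will reflect other therapy. The marking shows which, as far as medication records extend, and the unchanged 5-day count stays beside it.

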2.8.4 Other safety data**2.8.4.1 ECG and cardiac imaging data**

Not applicable, there are no ECG/cardiac imaging data.

2.8.4.2 Vital signs

The test values and the changes from baseline in vital signs (sitting/supine pulse rate, sitting/supine systolic blood pressure, sitting/supine diastolic blood pressure) will be summarized by vital sign parameter, age group and visit, using number of observations, mean, standard deviation, median, minimum, Q1, Q3, and maximum. By-visit summaries will only include scheduled assessments.

The number (percentage) of patients with clinically notable vital signs ([Table 2-5](#)) during the treatment period will be summarized by visit, separately by criteria and age group.

Table 2-7 Criteria for clinically notable vital signs

Age (years)	HR [min^{-1}]	SBP [mmHg]	DBP [mmHg]
1- <3	<60, >120	<76, >115	<45, >75
3- <6	<55, >120	<82, >120	<50, >80
6- <12	<50, >105	<90, >130	<50, >80

Age (years)	HR [min ⁻¹]	SBP [mmHg]	DBP [mmHg]
≥ 12	<45, >95	<90, >145	<55, >90

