**Table 3-2 Study drug dose levels for sacubitril/valsartan**

age groups 1 and 2 *	
Dose levels for pediatric formulation	
Dose level 1	0.8 mg/kg bid.
Dose level 2	1.6 mg/kg bid.
Dose level 3	2.3 mg/kg bid.
Dose level 4	3.1 mg/kg bid.
Dose levels for adult formulation	
Dose level 1	50 mg bid.
Dose level 2	100 mg bid.
Dose level 3	150 mg bid.
Dose level 4	200 mg bid.

\*Note: sacubitril/valsartan target dose (dose level 4) for age groups 1 and 2 is 3.1 mg/kg bid. (see [Section 4.2](#) for additional details).

If a subject is unable to tolerate up-titration to a higher sacubitril/valsartan dose level or at the discretion of the investigator, subjects may be maintained on lower dose levels of sacubitril/valsartan (dose level 1-3, see [Table 3-2](#)). In case of a consecutive 3-month interruption of study treatment, subject should be discontinued from the study and should complete Visit 599.

An outline of the study design is presented in [Figure 3-1](#). Depending on when and where the patient is enrolled, the duration of the study varies from 1 to approximately 4.5 years.

The OLE study drug starting dose will depend either upon the dose of ACEI/ARB that the subject was transitioned to after completion of the PANORAMA-HF or the dose the subject was on at the End of Study visit for the core study PANORAMA-HF prior to screening (Visit 500; refer to [Table 3-2](#)).

At Visit 501, subjects who meet eligibility criteria will start the study drug at dose level 1 or 2 ([Table 3-2](#)). Subjects who were on dose level 1 at the PANORAMA-HF End of Study (PANORAMA-HF visit 416) or who are on a low dose of ACEI/ARB (dose levels 1; [Table 3-3](#)) or not on an ACEI/ARB prior to screening (Visit 500) should start at dose level 1 at Visit 501.

[figure not shown]
Subjects who were on dose level 2, 3 or 4 at PANORAMA-HF visit 416 or who are on a higher dose of ACEI/ARB (dose levels 2, 3 or 4; [Table 3-3](#)) prior to screening (Visit 500) should start at dose level 2 at Visit 501 ([Table 3-2](#)) or at dose level 1 at investigator's discretion.

During the study, visits to assess safety will be conducted at Visit 501 and at 3-months intervals until the conclusion of the study (except for titration visits, which are at 2-week intervals). Unscheduled visits are allowed for subject's safety and for dose adjustment purposes

**Table 3-3 Total daily dose levels of commonly prescribed ACEI/ARBs for the purpose of comparing to dose levels of study drug**

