**Table 8-2 Physical Assessments**

Assessment	Specification
	A complete physical examination will include the examination of general appearance, skin, neck (including thyroid), eyes, ears, nose, throat, lungs, heart, abdomen, back, lymph nodes, extremities, vascular, and neurological. If indicated based on medical history and/or symptoms, rectal, external genitalia, breast, and pelvic exams will be performed.
Physical examination	An abbreviated physical exam will include the examination of general appearance and vital signs (systolic and diastolic blood pressure [SBP and DBP] and pulse) as well as other examinations based on the investigator's discretion. . Information for all physical examinations must be included in the source documentation at the study site. Clinically relevant findings that are present prior to signing informed consent must be recorded as medical history on the appropriate eCRF. Significant findings made after signing informed consent which meet the definition of an Adverse Event must be recorded as an adverse event on the corresponding eCRF.
Vital sign	Vital signs include BP and pulse measurements and are assessed when a complete or abbreviated physical examination is performed. After the subject has been sitting for approximately 5 minutes, with back supported and both feet placed on the floor, systolic and diastolic blood pressure will be measured using an automated validated device, e.g. OMRON, or a standard sphygmomanometer with an appropriately sized cuff on the non-dominant arm. Supine BP instead of sitting BP will be measured in subjects who are infants or who cannot sit comfortably. Clinically notable vital signs are defined in Appendix 1 .
Height, weight and head circumference	Height/ length in centimeters (cm). It is recommended to measure standing height using a stadiometer without shoes. Body weight (to the nearest 0.1 kilogram (kg) in indoor clothing, but without shoes) will be measured at every site visit. Body weight during hospitalization is to be recorded only if available as per standard of care. For subjects ≤ 3 years, head circumference in centimeters (cm) is measured.

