## 16.5 Appendix 5: American heart association (AHA) pediatric advanced life support (PALS) guidelines

**Table 16-7 5th percentile systolic blood pressure (SBP) table**

Age	SBP percentile	SBP (mmHg)
1 month to < 1 year	5 th	70
1 year	5 th	72
2 years	5 th	74
3 years	5 th	76
4 years	5 th	78
5 years	5 th	80
6 years	5 th	82
7 years	5 th	84
8 years	5 th	86
9 years	5 th	88
10 years	5 th	90
11 years	5 th	90
12 years	5 th	90
13 years	5 th	90
14 years	5 th	90
15 years	5 th	90
16 years	5 th	90
17 years	5 th	90

\* AHA PALS guidelines 2010 ([Kleinman et al 2010](#)) are widely used criteria for hypotension in acute HF patients. The formula (for 1 year and older: 70 mmHg + 2 x Age, up to age 10) is understood to provide the 5th SBP percentile up to 10 years. For children 1 month to < 1 year and >10 years, the AHA PALS guidelines 2010 5th percentile is set at 70 mmHg and 90 mmHg respectively. NOTE:

This formula approximates the population-based 5th percentile BP data; however, the margin of error increases with increasing age, with the PALS formula value generally providing a lower value.

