2.8.1.1 Adverse events of special interest / grouping of AEs

Most common TEAEs are defined as any recorded TEAE corresponding to a PT with at least 5% of patients having at least one TEAE of this PT. Most common TEAEs will be derived overall and by age group and will be summarized by age group and for overall, by SOC and PT, in descending frequency according to incidence, starting from the most common event.

[Table 2-1](#) shows the identified and potential risks for LCZ696 and the specifically specified analyses for each risk. In addition, the following standard analyses will be applied to all risks.

- Numbers and percentages of patients with any TEAE within the risk category (or SOC/PT within risk category) by age group and risk category, SOC, PT and maximum severity.
- Exposure adjusted incidence rates per 100 patient-years for TEAEs within the risk category by age group and risk category.
- Listing of patient numbers per risk.

Table 2-3 Identified and potential risks

Risk	Analysis
Hyperkalemia	1. Standard analyses; 2. Numbers and percentages of patients with treatment emergent hyperkalemia among patients with/without hyperkalemia at baseline by age group and overall 3. Numbers and percentages of patients with any post-baseline serum potassium ≥ 5.5 mEq/L, >6.0 mEq/L and >6.5 mEq/L by age group and overall
Hypotension	1. Standard analyses;

Risk	Analysis
	
2. Blood pressures and change from baseline in blood pressures will be summarized by visit, time point, age group and overall using number of observations, mean, standard deviation, median, minimum, Q1, Q3, and maximum;
 
3. Numbers and percentages of patients with the following events during the treatment period will be provided by age group and overall:
 
• Post-baseline systolic blood pressure (SBP) < 5th percentile per age (Table 16-7 in the protocol);• At least 20 mmHg drop in SBP (post-baseline assessments comparing to baseline);• Simultaneous treatment emergent symptomatic hypotension and postbaseline SBP < 5th percentile per age (Table 16-7 in the protocol);• Simultaneous treatment emergent symptomatic hypotension and at least 20 mmHg drop in SBP (post-baseline assessments comparing to baseline);• Simultaneous post-baseline SBP < 5th percentile per age (Table 16-7 in the protocol) and at least 20 mmHg drop in SBP (post-baseline assessments comparing to baseline).
Angioedema (positively adjudicated events)	Standard analyses;

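### Notable pulse, diastolic and high systolic values have no any-time patient count, and on a plain reading the by-visit table omits unscheduled visits

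*SAP*

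**What the plan says.** - SAP 2.8.4.2, first paragraph, describes summaries of values and changes from baseline and ends: "By-visit summaries will only include scheduled assessments".
- SAP 2.8.4.2, second paragraph, says that the number and percentage of patients with notable vital signs "during the treatment period will be summarized by visit, separately by criteria and age group". The criteria are low and high limits for pulse, SBP and DBP in four age bands. The text links to Table 2-5, but the table is captioned 2-7.
- SAP Table 2-3, Hypotension, item 3: "Numbers and percentages of patients with the following events during the treatment period will be provided by age group and overall". The first event listed is "Post-baseline systolic blood pressure (SBP) < 5th percentile per age (Table 16-7 in the protocol)". A second is a fall in SBP of 20 mmHg or more from its baseline value, and the list goes on to combinations, some of which involve symptomatic hypotension.
- SAP 2.8.3 counts notable laboratory values, liver events and renal events per patient over the treatment period, by criterion and age group.
- Protocol section 3: "Unscheduled visits are allowed for subject's safety and for dose adjustment purposes".
- Protocol Table 8-2: "Vital signs include BP and pulse measurements and are assessed when a complete or abbreviated physical examination is performed".
- Protocol 12.4 and SAP 2.5.1 list vital signs among the primary endpoints. Protocol 12.4 asks for vital signs and laboratory evaluations to be summarized by visit.

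**The concern.** There are two gaps. First, a by-visit table limited to scheduled assessments has no place for a reading taken at an unscheduled visit. Once titration is over, scheduled in-person visits are six months apart, so a transient abnormality may be seen only at an extra visit. Second, a by-visit table does not show how many patients were ever notable, even for scheduled readings. The SAP fills both gaps for laboratory values with a treatment-period count. It does not do so for vital signs, and it gives no reason for the difference. At stake is how completely a stated primary endpoint is reported: a reader of the study report could not tell what proportion of children had, for example, a notably low pulse at any time on treatment.

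**Working it through.** The plan states no figure to reproduce. The trial is a single-arm descriptive extension with no set sample size. The check therefore sets the planned counts side by side and then shows what a by-visit table can and cannot tell the reader.

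**1. Are vital signs recorded at unscheduled visits?** Protocol Table 8-2 ties them to any complete or abbreviated examination. Table 8-1 is broken in the text available. The vital-signs row has three marks left for its last four columns: a group of telephone visits, a group of site visits, unscheduled, and Visit 599. Blood pressure and pulse are not taken by telephone, so the three marks appear to belong to the other columns, including unscheduled. They are marked as database entries, not source-only.

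**2. Which Table 2-7 criteria have a per-patient count over the treatment period?**

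| Criterion | Any-time count in the SAP |
|---|---|
| Low SBP | Largely, through Table 2-3 |
| High SBP | None |
| Low DBP, high DBP | None |
| Low pulse, high pulse | None |

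Three parameters with two directions each give 6 criteria. Five have no such count.

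**3. How closely does Table 2-3 match the low-SBP criterion?** Its limit comes from protocol Table 16-7: "The formula (for 1 year and older: 70 mmHg + 2 x Age, up to age 10)", then 90 mmHg. The Table 2-7 lower limits are 76 mmHg (1 to <3 years), 82 (3 to <6) and 90 (6 and over).

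| Age (years) | Table 2-7 | Table 16-7 | Difference (mmHg) |
|---|---|---|---|
| 1 | 76 | 72 | 4 |
| 2 | 76 | 74 | 2 |
| 3 | 82 | 76 | 6 |
| 4 | 82 | 78 | 4 |
| 5 | 82 | 80 | 2 |
| 6 | 90 | 82 | 8 |
| 7 | 90 | 84 | 6 |
| 8 | 90 | 86 | 4 |
| 9 | 90 | 88 | 2 |
| 10 to 17 | 90 | 90 | 0 |

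At ages 10 to 17 the two limits coincide. At ages 1 to 9 a reading in a band of 2 to 8 mmHg is notable under Table 2-7 but is not below the Table 2-3 limit. The Table 2-3 counts are not by visit, so the scheduled-only sentence does not exclude unscheduled readings from them.

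**4. Can the any-time figure be read off the by-visit percentages?** No. A patient who stays for the full schedule has 14 scheduled in-person post-baseline visits: 502 to 505 (4), the odd-numbered visits 507 to 523 (9), and 599 (1). Take an assumed rate p of notable values at each visit, with every patient attending all k = 14.

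- Same patients every time: any-time proportion = p. With p = 2%, this is 2%.
- Independent visits: 1 - (1 - p)^k = 1 - 0.98^14 = 24.6%.
- No patient notable twice: k × p = 14 × 2% = 28%.

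Under independence, p = 1%, 5% and 10% give 13.1%, 51.2% and 77.1%. Correlation within patients would lower these. The rates are assumptions chosen only to show that one set of by-visit percentages fits very different any-time proportions. Unscheduled readings could only raise the any-time figure.

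**The case against.** The strongest counter-case has four parts.

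- **Low SBP is already handled.** Hypotension is the vital-sign risk that the protocol names, and Table 2-3 counts it per patient over the treatment period. This stands, and it limits the point to the other five criteria plus the band at ages 1 to 9. Pulse, DBP and high SBP are not among the risks named in protocol 4.5.
- **Adverse events are captured whatever the visit type.** A reader might infer that the scheduled-only rule tilts the trial's overall safety result towards no problem. The documents do not support that. The primary safety assessment is based on adverse events, and these are counted by date. What remains is that a vital-sign abnormality enters the AE tables only when it is judged to meet the AE definition, whereas a threshold table is meant to be independent of that judgement.
- **Unscheduled visits are not all held for sick children.** Protocol 6.5.1 also uses them to titrate upwards once a patient is stable, and scheduled visits include the titration visits and Visit 599 after early discontinuation. It is therefore not shown that the omitted readings are the most abnormal ones.
- **The scheduled-only sentence may not govern the notable-value table.** It closes the paragraph before, and protocol 12.4 asks only for by-visit summaries. The sentence is worded for by-visit summaries in general, so the plain reading covers the table, but this is open to argument. The absence of an any-time count does not depend on it. Nor is protocol 12.4 an obstacle: it treats laboratory values in the same sentence, and the SAP still added a treatment-period count for those.

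**Conclusion.** The point holds for high SBP, low and high DBP, and low and high pulse: no planned output gives the number of patients ever notable on these. On the plain reading, their values at unscheduled visits enter no threshold count. For low SBP it holds only in the band of 2 to 8 mmHg at ages 1 to 9.

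It would go too far to conclude that notable values at unscheduled visits are never counted, or that no any-time incidence is produced at all; the Table 2-3 counts contradict both.

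The direction is under-counting. The size is unknown, because the documents give neither the rate of notable values nor the frequency of unscheduled visits. The conclusion assumes that the scheduled-only sentence applies to the notable-value table (for the unscheduled part only) and that unscheduled vital signs are in the database, as Table 8-1 appears to show.

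**What to change.** Keep the by-visit table in SAP 2.8.4.2. Add one table with the number and percentage of patients who have at least one notable value for each Table 2-7 criterion at any post-baseline assessment, scheduled or unscheduled, during the treatment period, by age group and overall. State in the same section whether the scheduled-only sentence governs the by-visit notable-value table.

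The cost is one extra table from data already in the database, plus a sentence of SAP text. No data collection and no existing output changes.
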